5.9 Statistical considerations

5.9.1 Statistical design, method and analytical procedures

Case data will be analyzed using Excel and MATLAB or other standard statistical software package.

Overall number of subjects diagnosed with csPCa in the MRI/US arm will be compared to number of subjects diagnosed with csPCa using microUS targeted and systematic biopsy samples in the MicroUS and MRI/MicroUS arms (i.e. discounting the MRI targeted samples taken after blinding in the MRI/MicroUS arm). A non-inferiority threshold of 10% will be used. Assuming a csPCa detection rate of 43% in each group, 1082 subjects are needed for 90% power.

For the secondary fusion comparison overall number of patients diagnosed with csPCa will be compared between MRI/US Arm and MRI/MicroUS Arm with a non-inferiority threshold of 10%. Assuming a csPCa detection rate of 42% in the MRI/US Arm and 44% in the MRI/MicroUS Arm 358 subjects per group is required for 90% power.

Details of the design are presented in section 5.8.1.

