5.9.5 Pass/fail criteria

The primary outcome of the study will fail if the number of subjects diagnosed with csPCa is more than 10% lower than the number of subjects diagnosed with csPCa in the MRI/US arm. This will be quantified by testing against the lower two-sided 95% confidence interval bound for the difference.

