5.9.6 Criteria for the termination of the clinical investigation

The investigation may stop early for success if the primary objective is proven with $p < 0.0026$ at an interim analysis performed at 50% recruitment. This was calculated using O'Brien-Fleming bounds, and lowers the maximum p-value at final analysis from 0.025 to 0.024.

If the investigation is terminated early, no follow-up with subjects is required, since the standard of care for patients anticipating prostate biopsy is not affected by early termination.

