5.9.9 Procedures that take into account all data

Statistical analyses around study endpoints will not include data for subjects who are withdrawn (before or after their biopsy) or for whom the collected study data is incomplete.

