5.9.10 Treatment of missing, unused data

If a study subject withdraws from the main trial prior to imaging, his consent form will be retained, and the reason for exclusion of the data will be handwritten on the form as "withdrawn prior to imaging". Similarly, if a study subject withdraws from the main trial following his imaging, his consent form and CRF will be retained, and both will be marked "withdrawn following imaging".

This will allow data to be collected about the number of patients that withdrew from the investigation prior to the imaging procedure, and the number that withdrew after the procedure.

The same process will be applied to any circumstance of incomplete or incorrect data, with an indicator handwritten on his consent form and CRF to provide information about why the record is not used for analysis.

5.9.11 *Exclusion of data*****

Conditions that would result in the exclusion of data would be if any data verification activity showed that data was recorded on the CRF incorrectly, or if the pathology report showed any inconsistency with information on the CRF.

If such incorrect data was discovered, data for this subject will not be included in any analysis, and the CRF for the subject will be marked to indicate that the data is excluded.

5.9.12 *Subjects at multi-center investigations*****

This information is provided in section 5.8.3.7.

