Multiparametric MRI (mpMRI) targeted biopsy has been extensively studied as a solution to this problem and represents a clear improvement over systematic biopsy.¹⁸⁻²¹ According to a

Cochrane review on the subject, the addition of mpMRI targeting improved detection of csPCa by 5% over systematic biopsy in biopsy naïve men.²² A meta-analysis by Goldberg showed a greater impact with a 7-18% improvement.²³ Similar reductions in upgrading have also been demonstrated, lowering the upgrading rate on radical prostatectomy from 30% to 6.7%.¹⁴

Table 1 - Efficacy of additional mpMRI-directed samples over Systematic biopsy alone. Improvement in csPca detection ranges from 5% to 18% while overall detection rate ranges from 30%-61%.

| Study | MRI+Sys csPCa | Sys csPCa | Difference | Limitations |
|--|----------------------|------------------|---------------------|---|
| Cochrane meta-analysis ²² | 53% | 48% | 5% | |
| Goldberg et al. meta-analysis ²³ | N/A | N/A | 7-18% (11% in RCTs) | |
| Valerio et al. meta-analysis ²⁴ | 36% | 26% | 9% | Variability in csPCa definition and inclusion of prior neg biopsy |
| Kasivisvanathan et al. meta-analysis ²⁵ | 40% | 27% | 12% | Variability in csPCa definition and inclusion of prior neg biopsy |
| PRECISE ²⁶ | 35% | 30% | 5% | Targeted biopsy only on MRI |
| MRI-FIRST ¹⁸ | 37% | 30% | 7% | |
| PAIREDCAP ²⁷ | 61% | 52% | 9% | |
| PRECISION ²⁸ | 38% | 26% | 12% | No systematic samples in MRI group |
| PROMIS ⁴ | 37% | 22% | 15% | No MRI targeted biopsy |
| 4M ²¹ | 30% | 23% | 7% | In-bore MRI sampling rather than MRI/US fusion |
| ASIST ²⁹ | 33% | 27% | 6% | Active Surveillance population |

The mpMRI-informed diagnostic pathway

The American Urology Association, European Association of Urology, and National Comprehensive Cancer Network all recognize the use of mpMRI in order to improve the efficacy of the prostate biopsy procedure.³⁰⁻³² However, mpMRI targeted biopsy still misses small high grade cancers and up to 20% of GG2 cancers^{4,18,20}. These groups agree that mpMRI targeted biopsy should be combined with systematic biopsy in order to optimize the procedure, and that systematic biopsy should still be performed in the event of negative mpMRI but persistent clinical suspicion of cancer.

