The inclusion of mpMRI has altered the diagnostic pathway by requiring a cohort of expert radiologists specializing in prostate MRI to meet the demand. The care pathway has also required changes to include referral to radiology after (and, in some settings, before) initial consultation with the urologist.

These changes to the patient care pathway have introduced new sources of error and delayed diagnosis in many places. In the UK for example, the median time to diagnosis is 55.5 days.³³ At one prostate diagnostic clinic, the time-to-diagnosis was significantly lower in patients who did not receive mpMRI compared to those that did (15 vs. 22 days).³³ This discrepancy is greater in centers which have pre-existing resource constraints.

Variability in care has been exacerbated by the reliance on mpMRI due to significant and widespread inter-reader variability. Pickersgill et al. found poor agreement and poor accuracy among blinded radiologists for PI-RADS score and prediction of csPCa.³⁴ Similarly, Westphalen et al. found a large 27%-44% variability in the targeted detection rate (positive predictive value) of MRI-targeted biopsy across 24 imaging centers.³⁵ This increase in variability reduces confidence in the diagnostic process and may contribute to suboptimal results as mpMRI adoption increases. In the same way, the inclusion of MRI-derived data, along with the transfer of imaging data in pre-specified proprietary formats for fusion biopsy, adds complexity to the diagnostic pathway.

This represents a source of error. The magnitude of this error has yet not been well quantified, but is likely to be substantial outside recognized centers of excellence.

Further, mpMRI cannot be used in all men. Among the contraindications are several conditions that are prevalent within the population at risk, including implanted devices such as pacemakers and hip replacements (hip prostheses alone represent up to 4%³⁶), impaired kidney function (12%³⁷), and claustrophobia (3-5%³⁸). These men are not candidates for the mpMRI diagnostic pathway.

Micro-ultrasound imaging

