Data available (see Table 3) on this topic include a large 11-center, 1040-subject registry study performing a direct comparison to mpMRI which concluded that the two techniques provided similar sensitivity and negative predictive value.¹³ Various other single-center studies and meta-analyses have demonstrated similar rates of csPCa detection between mpMRI-guided and microUS-guided biopsy protocols.^{8,11,12,39,45,46}

Table 3 - Recent studies comparing microUS and mpMRI

| Study | Metric | MRI | MicroUS |
|---------------------------------|-----------------------------|-----|---------|
| Klotz et al. ¹³ | Sensitivity | 90% | 94% |
| Wiemer et al. ¹² | csPCa detection | 38% | 44% |
| Lughezzani et al. ¹¹ | csPCa detection | 35% | 35% |
| Socarrás et al. ⁴⁵ | csPCa detection | 28% | 24% |
| Abouassaly et al. ⁸ | Increase in csPCa detection | N/A | 12% |

Calculation of Non-Inferiority Threshold and Expected Detection Rates

The non-inferiority threshold of 10% was determined by expert-consensus from the advisory panel involved in the creation of this protocol, however it is consistent with the improvement in csPCa rates observed in the literature for mpMRI over the previous standard of systematic biopsy (see Table 1). The expected csPCa rates across the three arms of 42-44% were calculated based on pooled data from 414 biopsy naïve subjects with combined microUS and mpMRI biopsy across 4 studies at 7 institutions. This data includes 1 previously published study¹¹ and 3 studies which have been submitted for publication, and correlates well with the data from Table 1.

Evaluation of hazards, risks and safety measures

Risks associated with the biopsy procedure are well understood and outside the scope of this protocol since the biopsy procedure is clinically indicated and study procedures are not expected to modify these risks. Risks associated with study data collection will be managed by the Study Monitor, as described in this CIP.

Statistical and weighting methods

All clinical studies were weighted based on enrollment numbers, unless otherwise stated or specifically excluded for differences in protocol or enrollment. Care was taken to identify studies with patients drawn from the same population which would not be independent.

Conclusions

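### The unadjusted primary non-inferiority test is valid, but prespecified adjustment for PSA and DRE could tighten its confidence interval at almost no cost

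*Combined protocol and SAP*

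**What the plan says.** Section 5.7.1 defines the primary outcome as a difference in the detection rate of Grade Group > 1 cancer. Section 5.9.1 describes the comparison as "Overall number of subjects diagnosed with csPCa in the MRI/US arm will be compared to number of subjects diagnosed with csPCa" on microUS targeted and systematic samples in the MicroUS and MRI/MicroUS arms together. It sets a 10% threshold and assumes 43% detection in each group. Section 5.9.5 gives the decision rule: "This will be quantified by testing against the lower two-sided 95% confidence interval bound for the difference". Section 5.9.6 adds a look "at an interim analysis performed at 50% recruitment", with p < 0.0026 for early success and 0.024 at the final analysis.

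No part of section 5.9 in the supplied text names a regression model, a baseline covariate, a site term or the method for the confidence interval. Section 5.9.12 only refers back to the number of subjects per site.

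Section 5.8.3.1 admits men because of elevated PSA and/or abnormal DRE. Section 5.8.6 lists what the CRF records under broad headings (demographics, genitourinary history, biopsy notes, survey). PSA and DRE are not named there.

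Two exclusion rules bear on any added covariate. Section 5.9.9 drops men "for whom the collected study data is incomplete", and section 5.9.11 drops a man if "data was recorded on the CRF incorrectly".

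**The concern.** The trial succeeds or fails on the lower limit of one confidence interval. The width of that interval depends partly on variation between men that is already present at baseline. If PSA, DRE result and age predict csPCa, a prespecified adjusted estimate of the same risk difference has a smaller standard error, and no extra men are needed. The plan admits men on PSA and DRE but makes no analytic use of them. What is at stake is some precision and a little power, not the validity of the result.

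**Working it through.** **Inputs.** Rates 43% v 43% and margin 0.10 (5.9.1, 5.9.3); 600 v 600 for the primary comparison, being 600 against 200 + 400 (5.9.2); one-sided 0.024 at the final analysis (5.9.6), so z = 1.977. R² is the share of outcome variance explained by the covariates. The documents give no value, so a range is shown.

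**The plan's own figure.** Unadjusted two-proportion size per group:

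n = 2 × 0.43 × 0.57 × (1.977 + 1.282)² / 0.10² = 520.6.

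With the continuity correction, n/4 × [1 + √(1 + 4/(0.10 n))]² = 540.4, which rounds up to 541 per group, or 1082 in total. This matches the stated figure exactly. At one-sided 0.025 without the correction the result is 516 per group (1032). The stated size is therefore consistent with an unadjusted analysis and does not rely on covariates.

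**Unadjusted analysis at 600 v 600.** SE = √(2 × 0.43 × 0.57 / 600) = 2.858 points. The 95% half-width is 1.96 × 2.858 = 5.60 points. Power = Φ(10/2.858 − 1.977) = Φ(1.521) = 93.6%.

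**With adjustment.** SE = 2.858 × √(1 − R²). Power = Φ((10 + d)/SE − 1.977), where d is the true microUS minus MRI/US difference in points. The last column is the unadjusted size per group with the same precision, 600/(1 − R²).

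| R² (assumed) | SE | Half-width | Power, d = 0 | Power, d = −2 (stress test) | Equivalent n per group |
|---|---|---|---|---|---|
| 0 | 2.858 | 5.60 | 93.6% | 79.4% | 600 |
| 0.02 | 2.830 | 5.55 | 94.0% | 80.2% | 612 |
| 0.05 | 2.786 | 5.46 | 94.7% | 81.4% | 632 |
| 0.10 | 2.712 | 5.31 | 95.6% | 83.5% | 667 |
| 0.17 | 2.604 | 5.10 | 96.9% | 86.3% | 723 |

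**Error rate.** In simulation, a standardised logistic model with PSA, DRE and age rejected in 2.2–2.6% of trials at a true −10 points (nominal 2.4%) and did not lose power. A least-squares version with 16 sites, PSA and DRE reduced the variance by 3–14% when there was no true difference.

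**Site terms.** Two spreads in section 5.20 might suggest a site effect: "27%-44% variability in the targeted detection rate" between imaging centres, and "while overall detection rate ranges from 30%-61" per cent between studies. Treated as uniform, they give R² of (0.17²/12)/0.2451 = 0.010 and (0.31²/12)/0.2451 = 0.033. Even at those values, a simulated model with 11 site groups and age showed no measurable gain: power was 94.0 v 93.8% and 93.2 v 93.2%, with Monte Carlo error of 0.3–0.4 points. Estimating the site terms uses up what they recover.

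**The case against.** The strongest reply is that nothing is wrong. The test is valid, its power already exceeds 90%, and the choice of estimator is a matter of preference. The first two parts stand in full, which is why this is an optional improvement. The third stands only in part, because the gain is specific, costs little and keeps the same estimand and margin.

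The reply is also right that the benefit is unproven. R² is assumed, and selecting men on PSA and DRE may lower it. At 0.02 the gain is 0.4 power points.

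Four stronger readings are tempting, and the documents do not support them.

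- A reader might infer that the plan is underpowered because power is 79.4% when microUS is 2 points worse. Section 5.20 does say "The expected csPCa rates across the three arms of 42-44" per cent, but section 5.9.1 gives the 42% to MRI/US and the 44% to MRI/MicroUS, and the primary comparison assumes equal rates. A 2-point shortfall is a stress test, not the plan's expectation.
- A reader might infer that a multicentre trial needs site terms for precision. The two spreads measure other things: one is the yield of MRI-targeted biopsy, and the other runs across studies with differing csPCa definitions and populations. Neither establishes a site effect here.
- A reader might infer that PSA and DRE are not collected. The CRF list consists of broad headings, and it does not name the pathology result or the imaging scores either, although the endpoints need them. Silence there is not evidence of absence.
- A reader might infer that randomisation was not stratified. Parts of the document and the study schema were not available, so this cannot be said.

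**Conclusion.** This is an inexpensive improvement, not an error. The simple difference may stand as the primary analysis without harm to validity. That statement covers only the omission of covariates. It does not cover the exclusions after randomisation in sections 5.9.9 and 5.9.11, or the unnamed interval method.

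Adjustment for PSA, DRE and age would shorten the half-width by 0.05 to 0.50 points and add 0.4 to 3.3 power points at the plan's own rates, over R² from 0.02 to 0.17. In the 2-point stress test it adds 0.8 to 6.9 points. These figures assume all 1200 men are analysed, 43% detection, and variance falling in proportion to 1 − R². With weak covariates the gain is close to nil.

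The eligibility wording is and/or, so one of the two values could be missing for some men. The fix therefore needs a missing-data rule.

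**What to change.** Confirm that the CRF captures the PSA value and DRE result, or add both to section 5.8.6. Then prespecify in section 5.9.1:

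- The primary estimate is the standardised (marginal) risk difference, pooled microUS group minus MRI/US arm, from a logistic model with group, log PSA, DRE result and age, plus any factor used to stratify randomisation.
- The interval uses the influence-function variance with a small-sample correction, multiplying by n/(n − p), where p is the number of model coefficients. It is compared with −10 points at the section 5.9.6 levels (0.0026 interim, 0.024 final), with the same covariates at both looks.
- Missing log PSA is set to the overall mean with a missing indicator, and missing DRE is its own category. A covariate that is missing, or is corrected after an error, does not exclude a man under section 5.9.9 or 5.9.11.
- The unadjusted difference is reported as a sensitivity analysis.

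Do not add site groups for efficiency. If PSA and DRE cannot be recorded, keep the simple difference as primary, say so, and name its interval method.

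The cost is some SAP wording, slightly more analysis work and possibly two CRF fields. No extra patients or procedures are needed. The risk is extra specification for almost no return if the covariates prove weak.

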5.4.6 Medical procedures

Medical procedures to be performed in the study consist of subject preparation and imaging. The procedure will be the same for all subjects.

The detailed procedure is as follows:

1. Screening and consent visit (may be combined with visits 2 and/or 3):
 - a. Patient meets inclusion criteria
 - b. Patient willing to be randomized
 - c. Informed consent and randomization
2. Prior to biopsy (***MRI/US and MRI/MicroUS arms only***):
 - a. Radiologist reads and annotates mpMRI for use during Fusion biopsy
 - b. Annotated mpMRI is provided
 - i. ***MRI/MicroUS arm***: MRI is not shared with operator until unblinding
3. Biopsy visit:
 - a. Save sweep of prostate
 - b. (***MicroUS and MRI/MicroUS Arms***) Record suspicious regions (PRI-MUS 3+)
 - c. Standard of care biopsy
 - i. Including targeted and systematic samples
 - ii. Targeted samples must be potted and labeled separately per best practices
 - d. Standard post-biopsy follow-up

The subject is not required to come for additional clinic visits in the context of the study.

Further healthcare decisions and follow-up are outside the scope of this study. The subject's participation in the study is completed 7 days following the biopsy session when they will be asked to answer a short questionnaire on their experience.

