5.7.2 Hypothesis

Primary Hypothesis: The micro-ultrasound biopsy procedure is non-inferior to the mpMRI/US fusion biopsy procedure with a threshold of 10% and thus reduce the need for MRI prior to biopsy.

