5.9.2 Sample size

The trial will include 1200 subjects as per the table below.

| Endpoints | MRI/US Arm | MicroUS Arm | MRI/MicroUS Arm |
|--------------------------------------|------------|-------------|-----------------|
| Primary – MRI vs. MicroUS | 541 | | 541 |
| Secondary – Fusion Comparison | 358 | - | 358 |
| Minimum Sample Size (N=1082) | 541 | 183 | 358 |
| Proposed Sample Size (N=1200) | 600 | 200 | 400 |
| Proposed Randomization Ratios | 3 | 1 | 2 |

It is not anticipated that additional subjects will be required, however if a subject drops out before the biopsy procedure they may be replaced as described in section 5.8.1.6.

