5.9.3 Level of significance and power of the clinical investigation

Assuming a csPCa detection rate of 43% in each group, 1082 subjects are needed for 90% power to demonstrate that the lower bound of the two-sided 95% confidence interval is greater than the 10% non-inferiority threshold.

R and/or MATLAB software were used for sample size calculations.

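### Two-thirds of the primary microUS group comes from the MRI/MicroUS arm, and no planned analysis estimates csPCa detection in the MRI-free arm on its own

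*Combined protocol and SAP*

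**What the plan says.** **Primary comparison.** Section 5.9.1 sets the MRI/US arm against the "number of subjects diagnosed with csPCa using microUS targeted and systematic biopsy samples in the MicroUS and MRI/MicroUS arms", "discounting the MRI targeted samples taken after blinding in the MRI/MicroUS arm". The margin is 10%.

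**Sizes.** The table in 5.9.2 gives, for MRI/US, MicroUS and MRI/MicroUS in that order, "Proposed Sample Size (N=1200) | 600 | 200 | 400" and "Minimum Sample Size (N=1082) | 541 | 183 | 358". The allocation is 3:1:2.

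**Blinding.** For the MRI/MicroUS arm, 5.4.6 states that "MRI is not shared with operator until unblinding". Suspicious regions (PRI-MUS 3+) are recorded in both microUS arms, and this step is listed before the biopsy step. Targeted samples are potted and labelled separately. Neither 5.4.6 nor 5.8.1.2 (Avoiding bias) says whether the operator is masked to the allocated arm. Nothing says whether the systematic cores are taken before or after unblinding.

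**Endpoint.** Section 5.8.1.3 defines the microUS samples as targeted and systematic cores taken under microUS alone, without mpMRI.

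**Other comparisons of csPCa detection.** The powered secondary comparison is MRI/US v MRI/MicroUS (5.7.1, 5.9.1). The only subgroup analysis (5.9.8) compares men with and without a prior mpMRI inside the MicroUS arm.

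**Conclusion to be drawn.** Section 5.7.2 states that microUS is non-inferior and will "thus reduce the need for MRI prior to biopsy".

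**The concern.** The MicroUS arm is the only group randomised to a pathway with no study MRI, and that pathway is what the statement in 5.7.2 is about. In the pooled group it supplies one man in three. The other two have a study MRI that is opened in the course of their biopsy procedure.

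Withholding the MRI and discounting its cores protects against knowledge of the MRI findings. It does not protect against knowledge that a second sampling pass will follow, if the operator has that knowledge. An operator who expects MRI targets might take fewer microUS targets. One who knows that only microUS cores count in this comparison might take more. If any systematic cores are taken after unblinding, they are not MRI-targeted, so 5.9.1 as written would still count them, although 5.8.1.3 requires samples taken without mpMRI.

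If microUS detection differs between the two arms, the pooled difference describes neither setting. The planned analyses would not show it, because no estimate is produced for either component. The pass decision could then rest mainly on men who had an MRI, while the conclusion concerns men who would not.

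**Working it through.** **Inputs.** Arm sizes 600/200/400 (minimum 541/183/358) from 5.9.2. Detection 43% in each group, margin 10 points and lower bound of a two-sided 95% CI from 5.9.1 and 5.9.3. Final one-sided level 0.024 after the interim, from the termination criteria in 5.9.6. Between-arm differences in microUS detection are assumptions, because the documents give none.

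**1. The plan's own sample size.** Section 5.9.3 states: "Assuming a csPCa detection rate of 43% in each group, 1082 subjects are needed for 90% power".
- n per group = 2 × 0.43 × 0.57 × (z₁₋α + z₀.₉)² / 0.10².
- At one-sided 0.025 this is 515.1, so 516 (1032 in total). At 0.024 it is 520.6, so 521 (1042).
- With the Fleiss continuity correction, (n/4)(1 + √(1 + 4/(n × 0.10)))², the result at 0.024 is 540.4, so 541 per group and 1082 in total. This matches exactly, although the correction is not mentioned.
- The secondary figure of 358 per group (42% v 44%) also reproduces, at one-sided 0.025 without correction.

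The sample size is not in question.

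**2. Share of the pooled group.** 400/600 = 66.7%, or 358/541 = 66.2% at the minimum sizes. If microUS detection in the MRI/MicroUS arm differs from that in the MicroUS arm by d, the pooled estimate differs from the MRI-free value by (400/600) × d.

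**3. Effect on the decision when microUS alone is exactly 10 points worse (33% v 43%).**
- SE = √((0.43 × 0.57 + 0.33 × 0.67)/600) = 0.0279.
- False-pass probability = P(Z > 1.96 − shift/0.0279).

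| Assumed d | Shift in pooled estimate | False pass |
|---|---|---|
| 0 | 0 | 2.5% |
| +3 points | 2.0 points | 10.7% |
| +5 points | 3.3 points | 22.2% |

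**4. The pooling can err either way.** MRI/US is held at 43%, one-sided level 0.024. One component arm is lowered by the stated amount and the other kept at 43%.

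| Assumed deficit | MRI-free arm lower: pooled difference, P(pass) | MRI/MicroUS microUS cores lower: pooled difference, P(pass) |
|---|---|---|
| 5 points | −1.7 points, 83% | −3.3 points, 64% |
| 10 points | −3.3 points, 65% | −6.7 points, 21% |
| 15 points | −5.0 points, 42% | −10.0 points, 2% |

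In the second column a deficit in the pathway of interest is diluted. In the third, a pathway equal to MRI/US is failed because of the other arm.

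**5. What the existing arms can estimate.**
- MicroUS v MRI/US (200 v 600): SE = √(0.43 × 0.57 × (1/200 + 1/600)) = 0.0404. The 95% half-width is 1.96 × 0.0404 = 7.9 points. Power for the 10-point margin is P(Z > 1.96 − 0.10/0.0404) = 70%. At 183 v 541 it is 66%.
- MicroUS arm v microUS cores of the MRI/MicroUS arm (200 v 400): SE = √(0.43 × 0.57 × (1/200 + 1/400)) = 0.0429, half-width 8.4 points. The smallest difference detectable with 80% power is about 12 points. Power for a true 5-point difference is about 22%.

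**The case against.** The best defence is that pooling is deliberate and fits the stated outcome. Section 5.7.1 defines the primary outcome by technique, and 5.8.1.3 defines the endpoint by cores taken without mpMRI. The arms are randomised, the MRI is withheld, PRI-MUS 3+ regions are listed for recording before sampling, and the MRI-targeted cores are left out. The pooled 600 v 600 comparison has about 94% power, which the MicroUS arm alone cannot approach. All of this stands, and it is why the pooled analysis should remain primary. It narrows the route by which behaviour could differ between arms, but it does not close it, and it supplies no estimate for the MRI-free pathway.

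A reader might infer more than the documents support:

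- *That the operator knows MRI-guided cores will follow.* The plan is silent on masking to arm, and the schema announced in 5.8.1.1 is not shown in the available text. The supportable statement is that masking is not described.
- *That post-unblinding systematic cores are being counted.* The order is not stated, so this is possible but not established.
- *That the pooling favours microUS.* The direction is unknown. Fewer microUS cores in the MRI/MicroUS arm would work against non-inferiority.
- *That the plan claims MRI can be omitted.* Section 5.7.2 speaks of reducing the need for it.
- *That the statement in 5.7.2 should be made conditional on the MRI-free arm meeting the margin.* A simulation of the step 3 scenarios (400,000 runs, one-sided 0.025) shows a poor trade. Requiring only the point estimate to be within the margin lowers false passes from about 10.5% to 10% and from about 22% to 19%. Requiring the confidence bound lowers them to about 2%, but with no true difference the chance of making the claim falls from 94% to 69%.

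**Conclusion.** The concern holds as a gap in the planned analyses. It does not show that the primary analysis is wrong. Two-thirds of the primary microUS group comes from the MRI/MicroUS arm. The plan contains no csPCa estimate for the MRI-free arm against MRI/US or against the men it is pooled with. Masking to arm and the timing of the systematic cores are unstated. The 5.9.8 subgroup does not fill the gap, because both of its groups lie inside the MicroUS arm.

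That the pooled estimate moves by two-thirds of any between-arm difference is arithmetic. The false-pass rates of about 11% and 22% are illustrations. They need a difference in the favourable direction of 3 or 5 points and a true deficit exactly at the margin, and nothing in the documents says that either occurs.

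**What to change.** Keep the pooled primary analysis and add to 5.9.1:

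1. **MRI-free estimate.** A supportive difference in csPCa detection, MicroUS arm v MRI/US arm, with 95% CI. Report it beside the pooled result and use it when interpreting the statement in 5.7.2, without a formal gate.
2. **Component arms.** The difference in microUS-only csPCa detection between the MicroUS and MRI/MicroUS arms, as an estimate with 95% CI. Say in advance that a null result does not show that pooling is safe, since the half-width of about 8.4 points is close to the 10-point margin. Report PRI-MUS 3+ targets per man by arm and, if captured, microUS cores per man.
3. **Cores that count.** Count systematic cores in the primary analysis only if they were taken before unblinding, so that 5.9.1 matches 5.8.1.3.
4. **Disclosure.** State in 5.4.6 or 5.8.1.2 whether the operator is masked to arm and whether systematic cores precede unblinding.

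**Cost.** Some SAP wording and a little more analysis work on the arms already randomised, with no extra patients or procedures. The supportive estimate will be less precise than the pooled one (half-width 7.9 against 5.6 points). The source-data list in 5.8.6 does not name core counts or core timing relative to unblinding, so the sponsor should confirm that both are recorded.

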5.8.1.3 Endpoints

Primary endpoint

Number of men diagnosed with csPCa based on the pathology samples collected during the biopsy procedure through:

- MicroUS samples (targeted and systematic samples taken under microUS imaging only without mpMRI)
- mpMRI/US Fusion samples (targeted and systematic samples taken under conventional ultrasound imaging with mpMRI targets)

Secondary endpoints

As above, with the addition of combined results for men undergoing Fusion biopsy on the microUS system:

- mpMRI/MicroUS samples (targeted and systematic samples taken under microUS imaging with mpMRI)

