5.9.8 Specification of subgroups for analysis

A subgroup analysis is planned for men in the MicroUS arm of the study who deviate from protocol by having prior mpMRI available. This analysis will be used to demonstrate whether or not this group is consistent with the group of men in the MicroUS arm who are mpMRI naïve.

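### Could MRI-informed systematic cores enter the primary micro-ultrasound count because the plan's text gives no time of unblinding in the MRI/MicroUS arm?

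*Combined protocol and SAP*

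**What the plan says.** Section 5.9.1 compares the MRI/US arm with the MicroUS and MRI/MicroUS arms pooled. On the micro-ultrasound side it counts targeted and systematic cores, "discounting the MRI targeted samples taken after blinding in the MRI/MicroUS arm". For design it refers elsewhere: "Details of the design are presented in section 5.8.1".

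Section 5.8.1.3 defines the primary samples as "MicroUS samples (targeted and systematic samples taken under microUS imaging only without mpMRI". For the secondary endpoint it adds combined results, described as "mpMRI/MicroUS samples (targeted and systematic samples taken under microUS imaging with mpMRI".

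Section 5.4.6, step 2(b)(i), sets the rule for the MRI/MicroUS arm: "MRI is not shared with operator until unblinding". Step 3(b) has suspicious micro-ultrasound regions recorded in that arm. Step 3(c) then covers the biopsy in one entry, "Including targeted and systematic samples", and asks for targeted cores to be potted and labelled separately. Step 3 has no separate line for unblinding.

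Section 5.8.1.1 announces a study schema. The figure is not shown in our copy.

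**The concern.** Three things look unsettled.

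- Section 5.4.6 does not place unblinding before or after the systematic cores.
- Section 5.9.1 uses the MRI/MicroUS arm in both comparisons. If each man has one set of systematic cores, those cores seem to be described in 5.8.1.3 both as taken without MRI and as taken with it.
- Section 5.9.1 removes only the MRI-targeted cores and says they are taken after blinding, which cannot be meant literally.

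The primary hypothesis (5.7.2) is that micro-ultrasound can reduce the need for MRI before biopsy. If an operator who had seen the MRI steered systematic cores towards a lesion, MRI yield would be credited to micro-ultrasound, which favours a false finding of non-inferiority. If the operator steered them away from an area to be sampled separately, the effect would run the other way and cost power. The arm concerned is 400/600 = 67% of the micro-ultrasound group (358/541 = 66% at the minimum size).

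**Working it through.** **The plan's own figures.** Inputs from 5.9.1 to 5.9.3 and 5.9.6: 43% in each primary group, a margin of 10 (taken as percentage points), 90% power, and a final one-sided level of 0.024 after the interim analysis.

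- Primary: n = 2 × 0.43 × 0.57 × (z0.976 + z0.90)² / 0.10² = 520.6. With continuity correction, (n/4) × [1 + √(1 + 4/(0.10 n))]² = 540.4, so 541 per group and 1082 in total, as stated.
- Secondary: (0.42 × 0.58 + 0.44 × 0.56) × (z0.975 + z0.90)² / (0.10 + 0.02)² gives 358 per group, as stated.

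Neither calculation uses the time of unblinding.

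**The passages side by side.** Suppose each possible order in turn.

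1. *Systematic cores before unblinding.* They are taken without MRI, as 5.8.1.3 requires. Section 5.9.1 counts them and drops only the later MRI-targeted cores. The secondary endpoint then adds the MRI-targeted cores to everything before them, which fits its introduction as combined results. All three sections agree.
2. *Systematic cores after unblinding.* They fail the primary definition in 5.8.1.3, yet 5.9.1 counts systematic cores from this arm. The sections would contradict each other.
3. *Two sets, one on each side of unblinding.* Section 5.4.6 gives no number of sets. Under 5.8.1.3 only the first set would be primary, and the count would still be micro-ultrasound only.

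Only the second order makes the sections clash, and nothing in the text calls for it. On any reading, 5.8.1.3 keeps a core taken with MRI knowledge out of the primary samples. Step 3(b) has the micro-ultrasound findings recorded in this arm, and separate potting lets the analyst identify the MRI-targeted cores to remove.

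**The wording slip.** An operator still blinded to the MRI cannot take MRI-targeted cores, so the phrase in 5.9.1 can only mean after unblinding.

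**Can a leak be sized?** Subtracting 43% from the 44% planned for the MRI/MicroUS arm, to get a 1-point MRI contribution, does not work. Section 5.9.1 uses 43% as a common rate for both primary groups, the MRI/US arm included, and then, for the secondary comparison: "Assuming a csPCa detection rate of 42% in the MRI/US Arm and 44% in the MRI/MicroUS Arm". The 43% is therefore not shown to be a micro-ultrasound-only rate.

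What remains is an assumption with a range. Suppose MRI knowledge raised counted detection by δ in the 400 men, with the true rates at the margin (43% against 33%). The pooled shift is δ × 400/600. The false non-inferiority rate is Φ(shift/SE − 1.96), with SE = √[0.43 × 0.57/600 + p(1 − p)/600] and p = 0.33 + shift.

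| δ assumed (points) | Pooled shift (points) | False non-inferiority rate |
|---|---|---|
| 0 | 0 | 0.025 |
| 1 | 0.7 | 0.043 |
| 2 | 1.3 | 0.069 |
| 3 | 2.0 | 0.106 |
| 5 | 3.3 | 0.219 |

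In the other direction, a 1-point loss in the 400 men at equal 43% rates lowers power from 94% to 90%. The documents support no particular δ, and the order that the sections imply makes it zero.

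**The case for a change.** The best case for a change is that intent is not procedure. Section 5.1 foresees 12 to 20 institutions, and sites could take the systematic cores on either side of unblinding without breaching 5.4.6 as worded. An analyst who opened only 5.9.1 would count every systematic core, whenever taken. The table shows that even a few points would matter, and falling back on the 200 MicroUS-arm men alone would be costly: SE = √(0.43 × 0.57/600 + 0.43 × 0.57/200) = 0.0404, and power = Φ(0.10/0.0404 − 1.96) = 70%, against 94% with 600 per group. The plan also treats MRI exposure as worth examining elsewhere, in 5.9.8: "A subgroup analysis is planned for men in the MicroUS arm of the study who deviate from protocol by having prior mpMRI available".

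Part of this stands. No sentence in the text we hold fixes the order, and one would help sites. The rest does not carry. Section 5.9.1 sends the reader to 5.8.1, which contains both the primary sample definition and the schema, so reading 5.9.1 alone is not following the plan. The schema is a natural place for the order, and its absence from our copy cannot be held against the plan. Section 5.9.8 concerns protocol deviations in a different arm. The MRI/MicroUS arm has MRI by design, and 5.4.6 does state who may see it and until when.

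**Conclusion.** No change to the plan is needed. Sections 5.4.6, 5.8.1.3 and 5.9.1, taken together, yield a micro-ultrasound-only count for the primary comparison, and an analyst would apply it without difficulty. The two descriptions in 5.8.1.3 belong to different endpoints, the second building on the first, and the slip in 5.9.1 misleads nobody. No bias in the planned analysis is shown, no size can be derived from the documents, and 541 and 358 per group are unaffected. The sponsor could align the three passages with the schema when the text is next edited; the order is the sponsor's to state.

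This rests on two assumptions: that 5.8.1.3 governs which cores count as primary, and that neither the schema nor site practice places the counted systematic cores after unblinding. Evidence against the second would reopen the question, because it would affect two thirds of the micro-ultrasound group.
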